## 9.6 Definition of On-treatment Period

The on-treatment period is defined as the time from the first dose of study intervention day to the last administration day of study intervention + 30 days, or the cut-off date or death, whichever occurs first.

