5.2 Exclusion Criteria

Participants are excluded from the study if any of the following criteria apply:

Medical Conditions

1. Clinically significant (i.e., active) uncontrolled intercurrent illness including, but not limited to:
 - Active infection (i.e., requiring systemic antibiotics or antifungals)
 - Uncontrolled arterial hypertension (i.e., systolic blood pressure > 150 mmHg, diastolic blood pressure > 100 mmHg)
 - Symptomatic congestive heart failure (\geq New York Heart Association Classification Class II), unstable angina, myocardial infarction or a coronary revascularization procedure within 180 days of study entry
 - Calculated average QT interval corrected using Fridericia's formula (QTcF) of > 450 msec for males and > 470 msec for females.
 - A history of additional risk factors for Torsades de Pointes (e.g., clinically relevant hypokalemia, family history of Long QT Syndrome)

- The use of concomitant medications that prolong the QT/QTc interval
- Severe cardiac arrhythmia requiring medication
- Cerebral vascular accident/stroke
- Clinically significant liver disease consistent with Child Pugh Class B or C; and/or
- Any psychiatric illness/social situations that would limit compliance with study requirements.

2. Presence of brain metastases unless clinically stable (without evidence of progression by imaging for at least four weeks prior to the first dose of study intervention and any neurologic symptoms have returned to baseline), no evidence of new brain metastases, and on a stable or decreasing dose or without steroids for at least 14 days prior to study intervention. Participants with carcinomatous meningitis are excluded regardless of clinical stability. Central nervous system imaging at Screening is not mandatory.
3. Has a known additional malignancy that is progressing and/or requires active treatment. In addition, participants are excluded who were diagnosed with another malignancy within 3 years of starting study intervention. Exceptions include fully resected basal cell carcinoma of the skin or squamous cell carcinoma of the skin, *in situ* cervical cancer, fully resected ductal carcinoma *in situ*, and Stage IA noninvasive grade I endometrioid endometrial cancer, that has undergone curative therapy. Participants with other localized malignancies treated with curative intent need to be discussed with the Medical Monitor. Participant must not have any known history of myelodysplastic syndrome or acute myeloid leukemia.

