9.4 Statistical Analyses

All analyses will be prepared by DL and will be described in detail in the iAP. Except for the analysis of DLTs, all analyses will be performed on the Safety Analysis population.

The following statistics will be used to summarize the study data (e.g. baseline characteristics) unless otherwise specified:

- **Continuous variables:** number of non-missing observations, mean, standard deviation, median, 25% Percentile to 75% Percentile (Q1 to Q3), minimum, and maximum, 95% CIs for the mean, as appropriate.

- **Categorical variables:** frequencies and percentages.

The calculation of proportions will be based on the number of participants in the analysis set of interest, unless otherwise specified in the study iAP.

Baseline is defined as last non-missing value prior to first administration of study intervention

On-treatment values are defined as those measured during the study intervention period.

Besides the details outlined below, more details will be specified in the iAP finalized before database lock.

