## 9.2 Definition of Baseline and Change from Baseline

### Definition of baseline:

#### Part 1A:

In general, the last non-missing measurement prior to the first study intervention administration will be used as the baseline measurement.

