#### Part 1B:

In general (if not otherwise specified), the last non-missing measurement prior to the first study intervention administration will serve as the baseline measurement for efficacy as well as for safety analyses (irrespective of dietary status).

For food effect analyses on pre-defined endpoints, the 'baseline' refers to the last scheduled measurement before administration of study intervention in each food effect assessment period. However, if a participant is missing the baseline collection, the previous non-missing evaluation could become the baseline value (e.g. from screening/admission). If no baseline value exists, then the baseline value and the respective change from baseline will be treated as missing.

If an assessment that is planned to be performed before study intervention per protocol is performed on the same day as the start of study intervention, but the assessment time is not available, it will be assumed that it was performed prior and will be considered as baseline.

If a scheduled pre-dose measurement actually occurred post-dose, then the corresponding measurement will be analyzed similar to an unscheduled post-dose measurement.

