$$\text{Derived differential absolute count} = (\text{WBC count}) * (\text{Differential \%value} / 100)$$

If the range for the differential absolute count is not available (only range for value in % is available) then Grade 1 will be attributed to as follows:

- Lymphocyte count decreased:
  - derived absolute count does not meet Grade 2-4 criteria, and
  - % value < % LLN value, and
  - derived absolute count  $\geq 800/\text{mm}^3$
- Neutrophil count decreased:
  - derived absolute count does not meet Grade 2-4 criteria, and
  - % value < % LLN value, and
  - derived absolute count  $\geq 1500/\text{mm}^3$

For **calcium**, CTCAE grading is based on Corrected Calcium and Ionized Calcium (CALCIO), if available. Corrected Calcium is calculated from Albumin and Calcium as follows

$$\text{Corrected calcium (mmol/L)} = \text{measured total Calcium (mmol/L)} + 0.02 (40 - \text{serum albumin [g/L]})$$

**Liver function tests:** Alanine aminotransferase (ALT), aspartate aminotransferase (AST), and total bilirubin (TBILI) are used to assess possible drug induced liver toxicity. The ratios of test result over upper limit of normal (ULN) will be calculated and classified for these three parameters during the on-treatment period.

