#### Parameters with NCI-CTC grades available:

The laboratory toxicities will be tabulated using descriptive statistics (number of participants and percentages) during the on-treatment period. The denominator to calculate percentages for each laboratory parameter is the number of participants evaluable for CTCAE grading (i.e. those participants with normal values or for whom a Grade 1, 2, 3 or 4 can be derived). Grade 0 is not defined per NCI-CTCAE but will be used in derivations for simplicity to indicate that evaluable measurements are available.

- The summary of laboratory parameters by CTCAE grade table will include number and percentage of participants with Grade 1, 2, 3, 4, 3/4, and any grade (1 to 4), laboratory abnormalities during the on-treatment period.
- The shift table will summarize baseline CTCAE grade versus the worst on-treatment CTCAE grade. The highest CTCAE grade during the on-treatment period is considered as the worst grade for the summary.
  - In case of gradings involving baseline measurements (see Section 9.10) for the identification of grades during the on-treatment period, the shift table will present baseline normal and abnormal. Normal will include measurements below and within normal range (direction increase), or measurements within and above normal range (direction decrease).

The above analyses apply to hematology and chemistry evaluations which can be graded per CTCAE, i.e.:

Hematology:

- Hemoglobin (HB), Leukocytes (white blood cell decreased), Lymphocytes (lymphocyte count increased/decreased), Neutrophils / Absolute Neutrophils Count (ANC) (neutrophil count decreased), Platelet Count (PLT) (platelet count decreased).

Serum Chemistry:

- Albumin (hypoalbuminemia), Alkaline Phosphatase (alkaline phosphatase increased), Alanine Aminotransferase (ALT) (ALT increased), Amylase (serum amylase increased), Aspartate Aminotransferase (AST) (AST increased), Total Bilirubin (blood bilirubin increased, Creatinine (creatinine increased), Creatine Kinase (CPK increased), Potassium (hypokalemia/ hyperkalemia), Sodium (hyponatremia/ hypernatremia), Calcium (hypocalcemia/ hypercalcemia), Glucose (hypoglycemia/hyperglycemia), Gamma Glutamyl Transferase (GGT) (GGT increased), Lipase (lipase increased).

Please see [Appendix 1](#) for a list of the NCI-CTC -gradable parameters.

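### SAP 9.6 opens the on-treatment period on the calendar day of first dose and does not exclude the same-day pre-dose baseline record, so that record can enter several worst-on-treatment laboratory, vital-sign and ECG summaries

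*SAP*

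**What the plan says.** **Window.** SAP 9.6: "The on-treatment period is defined as the time from the first dose of study intervention day to the last administration day", extended by 30 days and cut at data cut-off or death. It gives no clock time. Protocol 9.4 does not settle the first day: "On-treatment values are defined as those measured during the study intervention period".

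**Baseline.** SAP 9.2 for Part 1A: "the last non-missing measurement prior to the first study intervention administration will be used as the baseline measurement". Part 1B uses the same general rule. For a planned pre-dose assessment done on the first-dose day, the text under the Part 1B heading continues: "but the assessment time is not available, it will be assumed that it was performed prior and will be considered as baseline".

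**Schedule.** In Part 1A, Protocol Tables 1 and 3 place pre-dose vital signs and a pre-dose triplicate ECG on Day 1. The Day 1 laboratory sample may be drawn that day or up to 72 hours before dosing. In Part 1B the first dose is on Day -7, and Tables 2 and 4 schedule the same kinds of assessment then, with triplicate ECGs only for participants dosed fasted. Protocol 1.3 files early laboratory samples under the planned dosing day in the CRF.

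**Outputs.** For graded laboratory terms SAP 15.4 says: "The highest CTCAE grade during the on-treatment period is considered as the worst grade for the summary". For ALT, AST and total bilirubin: "The ratios of test result over upper limit of normal (ULN) will be calculated and classified for these three parameters during the on-treatment period". SAP 15.4 and 15.5 also report maximum and minimum on-treatment values with their changes from baseline. SAP 15.6.2 draws its ECG summaries from the on-treatment period and includes absolute QTcF and QRS categories.

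**The concern.** A value taken before any drug has been given cannot show a drug effect. If it also counts as on-treatment, the worst on-treatment result can never be better than baseline, improvement cannot appear in the graded shift table, and an abnormality present only before dosing is reported as occurring on treatment.

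Whether this happens to a participant would depend on logistics: a sample taken on the morning of dosing is counted, one taken the day before is not. If the flag is programmed from the visit label and not the draw date, early samples would be counted too.

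These tables describe laboratory, vital-sign and ECG findings, which are listed under the primary objective, and Part 1A cohorts are planned at three participants. Entry rules leave room for pre-dose abnormalities. There is no lymphocyte limit. Participants with liver metastases may enter with ALT or AST up to 5 x ULN and bilirubin up to 3 x ULN. The QTcF exclusion limits are "of > 450 msec for males and > 470 msec for females", so a woman may enter at 451 to 470 ms.

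**Working it through.** The plan gives no figure on this point to reproduce. The check applies the definitions record by record, then output by output.

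**1. Classifying records**

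| Record | Baseline (SAP 9.2) | In window (SAP 9.6) |
|---|---|---|
| Laboratory sample before dosing on the first-dose day | Yes | Yes |
| Laboratory sample 1 to 3 days earlier, last before dosing | Yes | No, by draw date |
| Pre-dose vital signs or triplicate ECG on the first-dose day | Yes | Yes |
| Planned pre-dose assessment that day, time missing | Yes, by assumption | Yes |
| Post-dose assessment | No | Yes |

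**2. Consequence.** Let b be the same-day pre-dose value and y1 to yk the later values in the window.
- Maximum on treatment = max(b, y1, ..., yk), so its change from b is at least 0.
- Minimum on treatment = min(b, y1, ..., yk), so its change from b is at most 0.
- Worst grade = max(grade of b, later grades), so it is never below the baseline grade.

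Without b in the window, none of these constraints applies.

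**3. Outputs affected**
- Worst grades and shift table for terms not graded relative to baseline, such as hemoglobin, neutrophils, lymphocytes, platelets, albumin and electrolytes.
- Laboratory and vital-sign maximum and minimum on treatment.
- The low/normal/high worst-value summary for non-gradable laboratory parameters.
- ULN ratios for ALT, AST and bilirubin. The eDISH plot, with reference lines at 3 x and 2 x ULN, states no window for its peaks.
- QTcF > 450, > 480 and > 500 ms, and QRS >= 120 ms, which also take triplicate averages.

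**4. Outputs not affected**
- Grades that depend on baseline (SAP 9.10): ALT, AST, ALP, GGT, bilirubin, creatinine, INR, eosinophilia. For ALT with an abnormal baseline, Grade 1 starts at 1.5 x baseline, and the baseline record is 1.0 x itself.
- Shifts from a normal baseline: a normal record cannot also be above or below normal.
- ECG categories that need a change (QTcF > 30 or > 60 ms, HR >= 20 bpm, PR >= 20 ms): the baseline's change from itself is 0.
- The ECG morphology shift, limited to post-baseline abnormalities.
- The vital-sign change categories, limited to after the start of study intervention.
- AESI reporting (eCRF events and the SMQ) and the DLT, BLRM and MTD analyses, which do not use these tables.

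**5. Size.** A count rises only if the abnormality is present pre-dose and not seen again:

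extra participants = N x p x q,

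with p the share abnormal on the first-dose day and q the share of those in whom it does not recur. The documents give neither; p = 10 to 40% and q = 10 to 50% are assumptions.
- N = 28: 28 x 0.10 x 0.10 = 0.3 to 28 x 0.40 x 0.50 = 5.6.
- N = 22: 22 x 0.10 x 0.10 = 0.2 to 22 x 0.40 x 0.50 = 4.4.
- One participant in a cohort of three: 1/3 = 33 percentage points.

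**6. How often baseline is the extreme.** If all k + 1 values were exchangeable and untied, the chance is 1/(k + 1): 25% for k = 3 (Days 2, 8, 15), 20% for k = 4 and 9% for k = 10. The k = 3 case omits the End of Study Intervention sample. If the estimated 105 days on study include 28 of screening and 30 of follow-up (an assumption), 105 - 28 - 30 = 47 treatment days remain. Days 2, 8, 15, 22, 29, 36 and 43 plus the end visit then give k = 8 and 1/9 = 11%.

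**The case against.** The best defence is that the SAP never says a baseline record is an on-treatment value and often treats the two as different things. SAP 9.2 sorts same-day records by actual timing: "If a scheduled pre-dose measurement actually occurred post-dose, then the corresponding measurement will be analyzed similar to an unscheduled post-dose measurement". That rule makes sense only if true pre-dose values are not post-dose data. The graded shift table sets baseline against worst on-treatment grade, SAP 15.4 speaks of grades at baseline and post baseline, and the ECG statistics are listed at baseline and at each post-baseline time point. A careful programmer could apply that intent. The endpoint in the protocol is also clinically significant change, and a baseline has no change from itself. The dated listings would make any overlap visible.

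Much of this stands as evidence of intent. It does not supply the missing rule. Only the vital-sign change categories and the ECG morphology shift restrict their data to after the start of dosing or to post-baseline. The graded laboratory tables, the maxima and minima, the ULN ratios and the absolute QTcF and QRS categories rely on the SAP 9.6 window alone and are not conditioned on change. Two programmers could follow the text and produce different tables.

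The limits on reach also stand. An abnormality that persists after dosing, such as a QTcF still above 450 ms, is counted with or without the overlap.

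**Conclusion.** The gap is real and worth closing, but its reach is limited. Applied as written, SAP 9.6 lets a same-day pre-dose record serve as both baseline and on-treatment value in the outputs listed as affected. The direction is known: worst values can only look worse and improvement is hidden. The size is uncertain. The range of 0.3 to 5.6 participants in 28 per parameter rests wholly on assumed prevalence and non-recurrence, and also on every sample being drawn on the first-dose day.

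A reader might infer more, and the documents do not support it:
- That the SAP deliberately counts baseline as on-treatment. It does not say so; the overlap follows from a date rule without an exclusion.
- That ECG results are affected generally. Only the absolute QTcF and QRS categories are.
- That 25%, or any 1/(k + 1), is an error rate. It is the chance that baseline is the extreme of exchangeable values. Grades are often tied and serial values correlated, and a count moves only when the abnormality does not recur.
- That cytopenia AESIs, DLTs or the MTD suggestion are distorted. They come from other data.

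**What to change.** Add to SAP 9.6:

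> For laboratory, vital-sign and ECG measurements, on-treatment values are those taken after the date and time of first dose. The record used as baseline, and any planned pre-dose assessment on the first-dose day with missing time, is not an on-treatment value.

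State that baseline here means the value before the first administration (Day 1 in Part 1A, Day -7 in Part 1B). The period-specific baseline before the second food-effect dose follows the first dose and stays on-treatment in the overall tables. Derive the flag from the actual sampling date and time, not the CRF visit label, and apply the same window to the eDISH peak values.

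The cost is a sentence or two in the SAP and one condition in the on-treatment flag, with no new data. The day-based window can stay as it is for adverse events and concomitant medication.

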## 9.7 Exposure time

**Duration of exposure to study intervention** = date of last dose of study intervention – date of first dose of study intervention +1.

## 9.8 Imputation of Missing Data

Unless otherwise specified, all data will be evaluated as observed, and no imputation method for missing values will be used.

In all participant data listings, imputed values will be presented, and imputed information will be flagged.

Missing statistics, e.g. when they cannot be calculated, should be presented as “nd”. For example, if n=1, the measure of variability (SD) cannot be computed and should be presented as “nd”.

Where tables are presented over different time points, the total of missing and non-missing observations at each time point should reflect the population still in the trial at that time. This does not apply when imputations are made beyond trial withdrawal. For example, if a participant is still in the trial at the time-point but with missing data, they should be counted in the number of missing observations.

The following table for imputation rules will be considered:

Disease history	
Incomplete dates for disease history (e.g. initial diagnosis date, date of documented, locally advanced, inoperable or metastatic disease diagnosis, date of response or progression in prior treatment) will be imputed as follows:
 

• If the day is missing, it will be imputed to the 15th day of the month.

• If both day and month are missing and the year is prior to the year of the first study intervention, the month and day will be imputed as July 1st.

-----------------	---

	
 
• If both day and month are missing and the year is same as the year of the first study intervention, the month and day will be imputed as January 1st.
 
• If the date is completely missing, no imputation will be performed.
 

Adverse events	
Incomplete AE-related dates will be imputed as follows:
 
 
• In case the onset date is missing completely or missing partially but the onset month and year, or the onset year are equal to the start of study intervention then the onset date will be imputed by the minimum of start of study intervention and AE resolution date (if not missing).
 
• In all other cases, the missing onset day or missing onset month will be imputed by 1.
 
• Incomplete stop dates will be imputed by the last day of the month (if day is missing only), if not resulting in a date later than the date of participant's death. In the latter case, the date of death will be used to impute the incomplete stop date.
 
• In all other cases, the incomplete stop date will not be imputed.
 

Previous and concomitant medication	For identification of previous or concomitant medications/procedures, no formal imputation will be performed on missing or incomplete dates. Rules presented in Table 3 will be used to define if a medication/procedure is considered as a previous, concomitant or both previous and concomitant medication/procedure.

**Table 3** Imputation rules for medication/procedure end dates

End date of medication/procedure			Imputation rule		
Day	Month	Year			
UNK	UNK	UNK	After study intervention start (ongoing)		
UNK	UNK	< Study intervention start (year)	Before study intervention start		
UNK	UNK	≥ Study intervention start (year)	After study intervention start		
UNK	< Study intervention start (month and year)		Before study intervention start		
UNK	≥ Study intervention start (month and year)		After study intervention start		
< Study intervention start (complete date)			Before study intervention start		
≥ Study intervention start (complete date)			After study intervention start		

UNK = Unknown

**Table 4** Rules to define previous and/or concomitant medications

Start date of medication/procedure			Imputation rule (see Table 3)	Medication/procedure		
Day	Month	Year				
UNK	UNK	UNK	Before study intervention start	Previous		
UNK	UNK	UNK	After study intervention start	Previous and concomitant		
UNK	UNK	$\leq$ Study intervention start (year)	Before study intervention start	Previous		
UNK	UNK	$\leq$ Study intervention start (year)	After study intervention start	Previous and concomitant		
UNK	UNK	$>$ Study intervention start (year) and $\leq$ Study intervention end + 30 days (year)	After study intervention start	Concomitant		
UNK	$\leq$ Study intervention start (month and year)		Before study intervention start	Previous		
UNK	$\leq$ Study intervention start (month and year)		After study intervention start	Previous and concomitant		
UNK	$>$ Study intervention start (month and year) and $\leq$ Study intervention end + 30 days (month and year)		After study intervention start	Concomitant		
$\leq$ Study intervention start (date)			Before study intervention start	Previous		
$\leq$ Study intervention start (date)			After study intervention start	Previous and concomitant		
$>$ Study intervention start (date) and $\leq$ Study intervention end + 30 days (date)			After study intervention start	Concomitant		

UNK = Unknown

Dates of study intervention	
Start date of study interventions:
 
 
• No imputation will be done.
 
 
End date of study interventions:
 
 
• In case the last date of study intervention is missing or incomplete the date of last administration of study intervention will be taken from the treatment termination eCRF pages.
 
• If the last date of study intervention is completely missing and there is no Treatment Termination eCRF page and no death date the participant should be considered to be ongoing and use the cut-off date for the analysis as the last dosing date
 
• If the last date of study intervention is completely or partially missing and there is EITHER and Treatment Termination eCRF page OR a death date available (within the cut-off date) then imputed last dose date is: = 31DECYYYY, if only Year is available and Year < Year of min (EOT date, death date)
 

-----------------------------	---

	
= Last day of the month, if both Year and Month are available and Year = Year of min (EOT date, death date) and Month < the month of min (EOT date, death date)
 
= min (EOT date, death date), for all other cases

Death date	
For the purpose of survival analyses partially missing death dates will be imputed as follows:
 
If only the day is missing, the death date will be imputed to the maximum of the (non-imputed) day after the date of last contact and the 15th day of the month.
 
Otherwise, it will not be imputed.

Tumor assessments	
All investigation dates (e.g. X-ray, CT scan) must be completed with day, month and year.
 
If there are multiple scan dates associated with an evaluation, i.e., radiological assessments occur over a series of days rather than the same day, the choice of date of assessment could impact the date of progression and/or date of response. If there are multiple scan dates associated with an evaluation, the earliest of the scan dates associated with the evaluation will be used as the date of assessment.
 
If one or more investigation dates for an evaluation are incomplete but other investigation dates are available, the incomplete date(s) are not considered for calculation of the assessment date and assessment date is calculated as the earliest of all investigation dates (e.g. X-ray, CT-scan).
 
If all measurement dates for an evaluation have no day recorded, the 1st of the month is used.
 
If the month is not completed, for any of the investigations for an evaluation, the respective assessment will be considered to be at the date which is exactly between the previous and the following assessment. If both a previous and following assessments are not available, this assessment will not be used for any calculations.

Dates of subsequent anti-cancer therapy	
Incomplete dates for start date of subsequent anti-cancer therapy (drug therapy, radiation, surgery) will be imputed as follows and will be used for determining censoring dates for efficacy analyses and in the derivation of the end of on-treatment period.
 
If only day is missing, it will be imputed as the last day of the month unless the end date of subsequent anti-cancer therapy is before that date. In that case, the incomplete anti-cancer therapy start date will be imputed as the end date of the anti-cancer therapy.

	If both day and month are missing, no imputation will be performed. Incomplete subsequent anti-cancer therapy stop dates will not be imputed.
--	--

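### SAP 9.8 imputes a last-dose date that contradicts the recorded month and year when a month-and-year date falls in a calendar year before the end-of-treatment or death date

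*SAP*

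**What the plan says.** The study-intervention row of the table in SAP 9.8 works in stages. The first source is the termination page, which is what this sentence goes on to name: "In case the last date of study intervention is missing or incomplete the date of last administration of study intervention will be taken from the". SAP 13 repeats this.

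The imputation proper has its own trigger, which requires that at least one of two sources be present: "If the last date of study intervention is completely or partially missing and there is EITHER and Treatment Termination eCRF page OR a death date". It then has three branches. Call the earlier of the EOT date and the death date the reference.

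1. 31 December of the recorded year, "if only Year is available and Year < Year of min (EOT date, death date").
2. The last day of the recorded month, on two conditions. The first concerns the year: "if both Year and Month are available and Year = Year of min (EOT date, death date"). The second is that the recorded month comes before the month of the reference.
3. The reference date itself: "min (EOT date, death date), for all other cases".

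The last-dose date feeds several outputs. The on-treatment period (SAP 9.6) ends at "the last administration day of study intervention + 30 days, or the cut-off date or death, whichever occurs first". Exposure duration (SAP 9.7 and 13) is last dose minus first dose plus 1. SAP 15.3.1 tabulates deaths within 30 days of the last dose.

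**The concern.** The first two branches follow one principle: the imputed date may not run past the end of the period that was recorded. One combination escapes it. If month and year are both known and the year is earlier than the reference year, branch 1 fails because more than the year is known, and branch 2 fails because the years differ. The catch-all then assigns a date outside the recorded month and outside the recorded year.

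The resulting ordering makes no sense: a site that recorded only 2021 gets 31 December 2021, while a site that recorded December 2021 gets a date in 2022.

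At stake are exposure duration, the end of the on-treatment period and the count of deaths within 30 days of last dose. The on-treatment period governs treatment-emergent status in Part 1A and the on-treatment laboratory and vital-sign summaries. With planned cohorts of 3 participants, one misplaced death or event is visible in a table by dose level.

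**Working it through.** The plan gives no figure to reproduce; this is a check of rule logic. The inputs are the three branches of SAP 9.8. The calendar dates below are illustrative. The comparison rule differs in one respect: branch 2 applies whenever the recorded year and month together precede the reference year and month.

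| Recorded last dose | Reference | Branch reached | SAP 9.8 gives | Comparison rule gives | Days too late |
|---|---|---|---|---|---|
| Nov 2022 | 10 Dec 2022 | 2 | 30 Nov 2022 | 30 Nov 2022 | 0 |
| 2021 only | 10 Jan 2022 | 1 | 31 Dec 2021 | 31 Dec 2021 | 0 |
| Dec 2021 | 10 Jan 2022 | 3 | 10 Jan 2022 | 31 Dec 2021 | 10 |
| Nov 2021 | 10 Jan 2022 | 3 | 10 Jan 2022 | 30 Nov 2021 | 41 |
| Dec 2021 | 20 Feb 2022 (death, no earlier EOT date) | 3 | 20 Feb 2022 | 31 Dec 2021 | 31 + 20 = 51 |

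**Completeness.** Every month-and-year date in 2021–2022 was paired with every daily reference date in those years, keeping pairs where the recorded month is not after the reference month. The two rules differ in 4380 of 9144 combinations. All of these have a recorded year before the reference year, and the shift is always later, by at least 1 day. These counts describe the rule; they do not estimate how often the case will occur.

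**Size if the EOT date tracks the visit.** Protocol Table 1 places the End of Study Intervention Visit within 7 days after last dose, with a +7 day window, so at most 7 + 7 = 14 days after it.
- A last dose on 30 November gives a visit by 14 December, in the same year, so branch 2 works.
- Only a December last dose can push the visit into the next year. It does so no later than 31 December + 14 days = 14 January.
- Measured from 31 December, the error is therefore 1 to 14 days.

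**Size if only a later death date exists** (December 2021, death 20 February 2022).
- The imputed last dose is the day of death, so the death counts as within 30 days. Under any day the record allows, it lies between 51 days (from 31 December) and 30 + 51 = 81 days (from 1 December) after last dose, so it should not count.
- The on-treatment period should end 30 days after 31 December, on 30 January 2022. Under the rule as written it runs to 20 February, where the cap at death stops it: 21 days longer.
- With an assumed first dose on 6 November 2021, exposure is 107 days (15.3 weeks) instead of 56 days (8.0 weeks).

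**The case against.** **The case is hard to reach, and this stands.** The termination page is consulted first. Protocol 6.4 requires intervention start and stop dates in the CRF, with compliance checked at each visit and tablets reconciled. The SAP modification history says only the final analysis will be performed, and SAP 9.1 runs it after full cleaning. About 40 participants are planned. The number affected may well be zero, and the documents give no count. The third stage of the row nevertheless expects incomplete dates to survive these steps, including participants with only a death date.

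**The rule is formally complete, and this also stands.** The catch-all assigns a value, so nothing is undefined. That the authors intended the end of the recorded month is an inference from branches 1 and 2, not something the text states. The defect is a wrong assignment.

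**A deliberate latest-possible-date policy does not explain it.** Branches 1 and 2 both stop at the end of the recorded period.

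**A reader might infer that relative dose intensity is always lowered.** The documents do not support this. SAP 13 sums the actual doses but does not say how a dosing record with an incomplete end date is summed. In the 6 November example, if 56 daily doses are counted, relative dose intensity is 56/107 = 52%. If doses are taken as daily dose times the imputed interval, it is 107/107 = 100%. The direction and size are not determined.

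**A reader might take the 51-day example as typical.** It requires that no EOT date precede the death, although treatment stopped in December. With an EOT date near the scheduled visit, the error is days, not weeks. The SAP does not define EOT date, so a later one cannot be excluded.

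**Visibility.** SAP 9.8 flags imputed values in listings, so the contradiction could be noticed. The flag does not correct the tables.

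**Conclusion.** The point holds on the literal text, and nothing elsewhere in the protocol or SAP repairs it. Whenever the case is reached, the imputed last dose is later than any date the record allows.

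The error is 1 to 14 days for a December last dose if the EOT date follows the end-of-intervention visit. It is larger, 51 days in the example, if only a later death date is available or the EOT date is late. Exposure duration is lengthened. The on-treatment window can be lengthened, subject to its cap at death or cut-off. A death can be wrongly counted as within 30 days of last dose, but only in the late-reference situation.

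The practical reach is small: a partial last-dose date, no complete termination-page date, and a year-end crossing must coincide. A reader might suspect an effect on dose escalation, but the documents do not show that DLT counts, the Bayesian logistic model or the food-effect comparison depend on this imputation. It is a minor drafting correction.

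**What to change.** Widen the condition of branch 2 and leave branches 1 and 3 as they are. With the reference being the earlier of the EOT and death dates, impute the last day of the recorded month when month and year are known and either (a) the recorded year is before the reference year, or (b) the years are equal and the recorded month is before the reference month.

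Only the misassigned case changes; year-only, same-year and same-month records keep their current values. The cost is one clause in the SAP and one line of derivation code, with no loss elsewhere.
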